#### 4.3.2 Toxicities that require discontinuation from protocol therapy

Protocol therapy should be discontinued if a patient experiences:

- Any CTC Grade 4 toxicity with the exception of:
  - CTC Grade 4 neutropenia of 5 days or fewer duration
  - CTC Grade 4 nausea/vomiting or diarrhea that resolves to Grade 3 or less within 72 hours despite optimal supportive care.
  - CTC Grade 4 laboratory abnormalities that can be readily corrected within 72 hours and do not result in hospitalization.
- CTC Grade 3 thrombocytopenia with hemorrhage
- CTC Grade 3 febrile neutropenia
- Hy's Law (AST or ALT >3x ULN with concomitant serum bilirubin >2x ULN and no alternate etiology)

#### 4.3.3 Management of Infusion Reaction

Since sEphB4-HSA contains only human protein sequences, it is unlikely to be immunogenic and to induce infusion or hypersensitivity reactions. Since sEphB4-HSA specifically binds to EphrinB2, this makes it less likely that such a reaction would occur. However, if such a reaction were to occur, it might manifest with fever, chills, rigors, headache, rash, pruritus, arthralgia, hypo- or hypertension, bronchospasm, or other symptoms. Prophylactic premedications will be administered as described in Table 4-2-1. Infusion reactions should be graded according to the CTCAE Version 5.0 guidelines. Treatment recommendations are provided below and may be modified based on local treatment standards and guidelines, as appropriate:

**NU Study Number:** NU 18U10

For Grade 1 symptoms: (Transient flushing or rash, drug fever < 38C). Remain at bedside and monitor subject until recovery from symptoms.

For Grade 2 symptoms: (Rash, flushing, urticarial, dyspnea, drug fever > 38C) Stop the sEphB4-HSA infusion, begin an i.v. infusion of normal saline, and treat the subject with 25 mg additional diphenhydramine (for total dose of 50 mg, considering prior premedication with 25 mg) i.v. (or equivalent) and/or acetaminophen; remain at bedside and monitor subject until resolution of symptoms. Corticosteroid therapy (e.g., hydrocortisone, PRN, or other Institutional standard) may also be administered as appropriate. Additional supportive care may be administered per Institutional standard practice. If the infusion is interrupted, then restart the infusion at 50% of the original infusion rate when symptoms resolve; if no further complications ensue after 30 minutes, the rate may be increased to 100% of the original infusion rate. Monitor subject closely. If symptoms recur then no further sEphB4-HSA will be administered at that visit. The amount of study drug infused must be recorded on the case report form (CRF). The following prophylactic premedications are required for future infusions: diphenhydramine 50 mg (or equivalent) and acetaminophen 650 mg (or equivalent). Corticosteroids (e.g., hydrocortisone or other Institutional standard) are also recommended, if clinically indicated. These premedications should be administered at least 30 minutes before additional sEphB4-HSA administration. Remain at bedside and monitor subject until recovery from symptoms.

For Grade 3 or Grade 4 symptoms: (grade 3: Symptomatic bronchospasm, with or without urticarial, requiring parenteral medications; allergy related edema/angioedema, hypotension OR grade 4: Anaphylaxis as defined as a life-threatening event characterized by the rapid onset of airway obstruction including bronchospasm, stridor, hoarseness, urticarial and/or hypotension): Immediately discontinue infusion of sEphB4-HSA. Begin an i.v. infusion of normal saline, and treat the subject as follows: Recommend bronchodilators, epinephrine 0.3 mg of a 1:1,000 solution for intramuscular administration, or 0.1 to 0.25 mg of a 1:10,000 solution injected slowly for i.v. administration, and/or diphenhydramine 50 mg i.v. with methylprednisolone 100 mg i.v. (or equivalent), as needed. Subject should be monitored until the investigator is comfortable that the symptoms will not recur. sEphB4-HSA will be permanently discontinued. Investigators should follow their institutional guidelines for the treatment of anaphylaxis. Remain at bedside and monitor subject until recovery from symptoms. In the case of late-occurring hypersensitivity symptoms (e.g., appearance of a localized or generalized pruritus within 1 week after treatment), symptomatic treatment may be given (e.g., oral antihistamine, or corticosteroids).

Severe infusion reactions, including fatal reactions, have been observed in mice (but not in monkeys). All clinical sites must have immediate access to emergency medications and equipment and staff trained in CPR in addition to the ability to rapidly transfer patients to an intensive care setting if a patient experiences a severe infusion reaction.

#### **4.4 Concomitant Medications/Treatments**

Required premedications are described in Table 4-2-1. There are no other known concomitant medications or treatments associated or recommended with sEphB4-HSA at this time.

In the absence of treatment delays due to adverse event(s), concurrent therapy for prostate cancer with the exception of ongoing androgen deprivation and anti-resorptive agents such as bisphosphonates or denosumab are not permitted. If a patient develops a single symptomatic or imminently dangerous metastasis (such as fracture or vertebral compression) then intervention with radiation therapy and/or surgery is permitted after discussion with the study PI. In this case, study drug would be held during the intervention and recommenced after

**NU Study Number:** NU 18U10

completion and recovery from any adverse effects. The hold on study drug should not exceed 4 weeks.

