**3.2 Exclusion Criteria**

3.2.1 Patients who have received more than 3 prior treatment therapies (life prolonging) for mCRPC are not eligible.

3.2.2 Patients who have had radiotherapy  $\leq 14$  days prior to entering the study are not eligible.

*Note: Palliative radiation therapy is allowed.*

3.2.3 Patients who have had systemic therapy for prostate cancer  $\leq 21$  days or 5-half lives (whichever is shorter) are not eligible.

*Note: Patients can receive a stable dose of bisphosphonates for bone metastases, including zoledronic acid, or denosumab before and during the study as deemed appropriate by the treating physician. Patients must continue Androgen Deprivation Therapy.*

3.2.4 Patients receiving any other investigational agents are not eligible.

3.2.5 Patients with Small cell carcinoma of the prostate are not eligible.

*Note: Neuroendocrine differentiation is permitted. If there is doubt about this and it is clinically indicated then a biopsy should be obtained to document histological differentiation.*

3.2.6 Patients who have a history of allergic reactions attributed to compounds of similar chemical or biologic composition to sEphB4-HSA are not eligible.

AND

Patients who have had prior exposure to compounds of similar chemical or biologic composition to sEphB4-HSA are not eligible.

3.2.7 Patients who have an uncontrolled intercurrent illness including, but not limited to any of the following, are not eligible:

- Ongoing or active infection requiring systemic treatment
- Symptomatic congestive heart failure (New York Heart Association Class III or IV congestive heart failure)
- Unstable angina pectoris
- Serious cardiac arrhythmia

3.2.8 Patients with uncontrolled hypertension (defined as systolic BP  $\geq 160$  mmHg or diastolic BP  $\geq 95$  mmHg) are not eligible.

*Note: Patients with a history of hypertension are allowed provided blood pressure is controlled by anti-hypertensive treatment*

3.2.9 Patients with Electrocardiogram (ECG) with QT interval (QTc)  $> 480$  msec are not eligible.

3.2.10 Patients with other malignancy that has progressed or has required active systemic treatment in the last 3 years.

**NU Study Number:** NU 18U10

*Note: Patients with basal cell carcinoma of the skin, squamous cell carcinoma of the skin that has undergone potentially curative therapy or carcinoma in situ or non-muscle invasive bladder cancer are not excluded.*

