#### **6.1.2 Disease Parameters by RECIST V1.1**

Measurable disease. Measurable lesions are defined as those that can be accurately measured in at least one dimension (longest diameter to be recorded) as  $\geq 20$  mm by chest x-ray, as  $\geq 10$  mm with CT scan, or  $\geq 10$  mm with CT scan, MRI, or calipers by clinical exam. All tumor measurements must be recorded in millimeters (or decimal fractions of centimeters).

*Note: Tumor lesions that are situated in a previously irradiated area should not be considered measurable unless they have demonstrated progression.*

Malignant lymph nodes. To be considered pathologically enlarged and measurable, a lymph node must be  $>15$  mm in short axis when assessed by CT scan (CT scan slice thickness recommended to be no greater than 5 mm). At baseline and in follow-up, only the short axis will be measured and followed.

Non-measurable disease. All other lesions (or sites of disease), including small lesions (longest diameter  $<10$  mm or pathological lymph nodes with  $\geq 10$  to  $<15$  mm short axis), are considered non-measurable disease. Bone lesions, leptomeningeal disease, ascites, pleural/pericardial effusions, lymphangitis of skin or lung, inflammatory breast disease, and abdominal masses (not followed by CT or MRI), are considered as non-measurable.

*Note: Cystic lesions that meet the criteria for radiographically defined simple cysts*

*should not be considered as malignant lesions (neither measurable nor non-measurable) since they are, by definition, simple cysts.*

*'Cystic lesions' thought to represent cystic metastases can be considered as measurable lesions, if they meet the definition of measurability described above. However, if non-cystic lesions are present in the same patient, these are preferred for selection as target lesions.*

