## 6.2 Assessment of primary endpoint

The assessment of the primary endpoint of confirmed PSA response rate is defined as the proportion of subjects who received at least 1 dose of the study drug achieving a post-treatment PSA partial response or complete response as defined by PSA response criteria in section 6.1.5

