#### **10.1 Sample size and Statistical and data analysis plan for the primary objective.**

To estimate **preliminary efficacy** we will assess PSA response rate (PR and CR) with a **Simon two stage minimax design**. We assume the undesirable overall response rate (null hypothesis) to be approximately 10% or less, and the alternate hypothesis suggesting success to be approximately 30% or more. Fifteen patients will be added in the first stage. If 2 or more respond, then an additional 10 patients will be added for a total of 25 evaluable patients. If not, we will stop the study after the first stage. The study will be assessed by the DSMC for excess toxicity at this point in time and stopped if DSMC finds excessive toxicity. If the second stage is completed, five or fewer successes will suggest failure and six or more responses a success of the entire study. This design has a Type I error rate of less than 5% and 80% or greater power. It has a 55% chance of stopping early after the first stage if the true response rate is 10% or less, and a total expected long run average sample size of n=19.5. See below, using Pass 11 software.

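### A PSA response first reached after on-study radiotherapy or surgery to a metastasis (allowed by 4.4) counts as a drug response toward the 2/15 and 6/25 cut-offs

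*Combined protocol and SAP*

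**What the plan says.** Section 4.4 bars other prostate cancer therapy apart from ongoing androgen deprivation and anti-resorptive agents, then makes an exception. If a single metastasis becomes symptomatic or imminently dangerous, "then intervention with radiation therapy and/or surgery is permitted after discussion with the study PI". Drug is stopped for the intervention and restarted after recovery: "The hold on study drug should not exceed 4 weeks". The patient stays on study and PSA continues to be measured.

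Section 6.2 defines the primary endpoint as the proportion of dosed patients "achieving a post-treatment PSA partial response or complete response as defined by PSA response criteria in section 6.1.5". Section 6.1.5 requires a fall of at least 50% (PR), or PSA at or below 0.2 ng/ml (CR), confirmed about 4 weeks later. Section 10.1 tests this PSA response: "We assume the undesirable overall response rate (null hypothesis) to be approximately 10% or less" against "the alternate hypothesis suggesting success to be approximately 30% or more". The interim rule is "If 2 or more respond, then an additional 10 patients will be added for a total of 25 evaluable patients", and six or more responses among 25 are a success.

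Section 6.1.1 requires a follow-up PSA before any subsequent therapy, but only as a condition of being evaluable. For RECIST, section 6.1.2 notes: "Tumor lesions that are situated in a previously irradiated area should not be considered measurable unless they have demonstrated progression".

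**The concern.** The primary endpoint is meant to measure what the drug does. Irradiating or removing a PSA-producing lesion can itself lower PSA. No sentence in 6.1.5, 6.2 or 10.1 separates a fall that began before the local treatment from one that began after it, so an analyst following the plan would count both. Nor does 6.1.1 say whether local treatment under 4.4, with drug restarted, is a subsequent therapy. Even if it were, that sentence settles who enters the denominator, not which PSA values may establish a response.

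With 25 patients and cut-offs of 2 and 6 responders, one patient can change either decision. At stake are continuing to stage 2, or declaring success, partly because of treatment that is not the study drug.

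A smaller gap affects the secondary overall response rate. Nothing says how to score a soft-tissue target lesion that is irradiated or resected during the study.

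**Working it through.** **Inputs from section 10.1:** n1 = 15, continue if at least 2 respond; n = 25, success if at least 6 respond; p0 = 0.10; p1 = 0.30.

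**1. Reproduce the design.** Let X1 ~ Bin(15, p) and X2 ~ Bin(10, p).

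- Early stopping: PET = P(X1 ≤ 1). At p = 0.10 this is 0.9^15 + 15 × 0.1 × 0.9^14 = 0.2059 + 0.3432 = 0.549.
- Average N = 15 + 10 × (1 − 0.5490) = 19.51.
- Success: S(p) = sum over x ≥ 2 of P(X1 = x) × P(X2 ≥ 6 − x). S(0.10) = 0.0328; S(0.30) = 0.8017.

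The plan's table gives PET 0.549, average N 19.51, alpha 0.033 and beta 0.198. All agree.

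**2. One or two miscredited patients, true rate 10%.** Treat the miscredited patient as a certain responder and let the others respond at 10%.

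- One in stage 1: PET falls to 0.9^14 = 0.229; S = 0.0847.
- One in stage 2: S = 0.0820.
- One at a random position: 15/25 × 0.0847 + 10/25 × 0.0820 = 0.084.
- Two at random positions: both in stage 1 (probability 0.35) 0.1927; one in each stage (0.50) 0.1908; both in stage 2 (0.15) 0.1786. Weighted result 0.190.

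**3. The same effect as a rate.** Let q be the share of patients treated locally on study, and s the share of those, among patients who would not otherwise respond, who then meet the PSA criterion. The apparent null rate is p* = 0.10 + 0.90 × q × s. The documents give neither q nor s; all values below are assumptions.

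| q | s | p* | S(p*) |
|---|---|---|---|
| 4% | 10% | 0.1036 | 3.8% |
| 4% | 25% | 0.109 | 4.7% |
| 8% | 25% | 0.118 | 6.5% |
| 10% | 30% | 0.127 | 8.7% |
| 10% | 50% | 0.145 | 14.1% |

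S(p*) reaches 5% at p* = 0.1105, that is q × s = 0.0105/0.90, or about 1.2% of non-responders miscounted.

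**4. Cost of not counting these responses.** If the rule lowered the apparent rate of an active drug from 30% to 29.5% (an assumption), power would go from 0.802 to S(0.295) = 0.786.

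**5. Overall response rate.** Section 10.2 reports it with a 90% interval and no cut-off, so it does not enter steps 1 to 4. Section 6.1.2 classes bone lesions as non-measurable, so they never enter the sum of diameters. Its note on irradiated areas governs which lesions are measurable; sections 6.1.6 and 6.1.9 do not deal with a target lesion treated later. The gap is confined to soft-tissue target lesions.

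**The case against.** The best reply is that this may seldom happen. Section 4.4 covers only one symptomatic or dangerous metastasis, and eligible patients have progressive metastatic disease with no limit on the number of lesions. Nothing in the documents shows that treating one lesion would halve total PSA and hold it there for the 4-week confirmation. Section 4.5 lists symptomatic progression as a reason to end treatment, which may remove some of these patients. The 8.4% and 19.0% figures assume that the miscredited responders exist; they show how sensitive 25 patients are to misclassification, not how likely this one is. All of that stands, and at the low end of the assumed range alpha stays below 5%. It limits the size of the problem but supplies no rule for the case when it occurs.

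Counting these responses and listing them would also be a defensible estimand, but the plan does not state that choice.

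Three stronger readings are tempting, and the documents do not support them:

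- That lesion shrinkage can help meet 2/15 or 6/25. Those cut-offs test PSA response only, and the examples in 4.4 (fracture, vertebral compression) point to bone.
- That local treatment under 4.4 is definitely not a subsequent therapy. Section 6.1.1 leaves the term undefined.
- That the note to 3.2.2, "Palliative radiation therapy is allowed", admits patients whose PSA is about to fall from recent radiotherapy. The note gives no timing and may refer to treatment outside the 14-day window. It is a separate wording issue.

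**Conclusion.** The gap in the primary endpoint is real and should be closed. As written, a PSA response first reached after local treatment under 4.4 counts for the drug. One such patient takes the false-success probability at a 10% true rate from 3.3% to about 8.4%; if that patient is in stage 1, the chance of stopping early falls from 54.9% to 22.9%. How often it would happen cannot be taken from the documents. Under the assumed rates the probability runs from 3.8% to 14.1%, so a reader should not infer that the stated limit of 5% is necessarily broken. For the overall response rate the point is minor: a missing scoring rule for locally treated soft-tissue target lesions, with no bearing on the go/no-go decisions.

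**What to change.** Whether local treatment is given stays with the investigators. The changes concern only how data are counted:

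- **6.1.5 and 6.2:** a PSA response whose first qualifying fall occurs after on-study radiotherapy or surgery to a metastasis is not counted in the primary analysis, and the patient stays in the denominator as a non-responder. A fall reached before local treatment and confirmed afterwards is not discarded by this rule but is flagged. A sensitivity analysis counts all responses affected by local treatment.
- **6.1.1:** state whether local treatment under 4.4 is a subsequent therapy.
- **6.3.3:** shrinkage or removal of a locally treated target lesion cannot establish CR or PR.
- **Case report form:** record the date and site of each intervention. Section 4.4 asks for PI discussion and a drug hold but does not say that these are captured.
- **3.2.2:** reconcile the exclusion and its note as a separate item.

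The cost is a few sentences and one form field, with no extra patients. The downside is that a genuine drug response first appearing after local treatment is lost from the primary analysis, with a small loss of power (0.802 to about 0.786 in the case shown). The sensitivity analysis would show any such patient.

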**4.5 Duration of Therapy**

Treatment may continue until one of the following criteria applies:

- No longer clinically benefiting (PCWG3, symptomatic or objective disease progression by RECIST v1.1 (See Appendix IV))
- Intercurrent illness that prevents further administration of treatment
- Unacceptable adverse event(s) as evaluated by the treating physician (see section 4.3)
- Therapy delay for  $\geq 4$  weeks
- Patient decides to withdraw from the study or elects to discontinue investigational therapy
- General or specific changes in the patient's condition render the patient unacceptable for further treatment in the judgment of the investigator

**4.6 Duration of Follow Up**

Patients removed from study for progression will return for an End of Treatment (EOT) visit 30 ( $\pm 3$ ) days of the last dose of study treatment or prior to initiating new therapy. Patients removed from study for unacceptable treatment-related adverse event(s) will be followed until resolution or stabilization of the adverse event. If off treatment for reasons other than disease progression, patients will be followed every 6 months, until objective progression or patient starts alternative therapy for a maximum of 1 year.

**4.7 Removal of Subjects from Study Treatment and/or Study as a Whole**

Patients can be taken off the study treatment and/or study as a whole at any time at their own request, or they may be withdrawn at the discretion of the investigator for safety, behavioral or administrative reasons. The reason(s) for discontinuation must be clearly documented on the appropriate eCRF and may include:

- Patient voluntarily withdraws from treatment (follow-up permitted)
- Patient withdraws consent (no follow-up permitted)
- Patient is unable to comply with protocol requirements
- Patient demonstrates disease progression
- Patient experiences unacceptable toxicity
- Treating physician determines that continuation on the study would not be in the patient's best interest
- Patient develops a second malignancy that requires treatment which would interfere with this study
- Patient is lost to follow-up (LT)

**4.8 Patient Replacement**

Any patient who signs consent and is registered for the trial but does not receive study treatment may be replaced.

## 5 STUDY PROCEDURES

Time Period	Screening (≤1 month unless otherwise indicated) 	On Treatment (1 Cycle = 14 Days)							Off Treatment	
		Cycle 1	Cycle 2	Cycle 3	Cycle 4	Cycle 5	Cycle 6	Cycle 7+ 	End of Treatment 	Follow -up 
Baseline	Week 1 Day 1	Week 3 Day 1	Week 5 Day 1	Week 7 Day 1	Week 9 Day 1	Week 11 Day 1	Week 13 Day 1			
Assessment or Activity										
Informed Consent	X									
Medical history 	X 								X 	
Physical exam 	X	X	X	X	X	X	X		X	
ECOG status	X	X	X	X	X	X	X		X	
Toxicity assessment		X	X	X	X	X	X		X	
Review Concomitant Medications	X	X		X		X			X	
Tumor Imaging 	X				X 				X	
CBC + diff, chemistry, liver enzymes *3, 4	X	X	X	X	X	X	X		X	
PSA *5	X	X		X		X			X	
EKG *6	X			X	As clinically indicated				As Clinically Indicated	
Research blood 	X					X			X	
Archival tissue sample 				X					X	
sEphB4-HSA administration 		X	X	X	X	X	X			
Survival Status										X

\*Can be completed  $\pm 3$  days of drug administration

- Includes vital signs (pulse, blood pressure) and height (baseline only) and weight.
- Bone scan, CXR or CT of chest, CT or MRI or abdomen and pelvis; with IV contrast if renal function adequate; the same modality used at baseline should be used throughout as clinically indicated. Imaging will occur at baseline and 2 months ( $\pm 7$  days) after starting therapy; thereafter, imaging will be conducted every 3 months ( $\pm 7$  days). After 1 year, imaging can be done every 4 months ( $\pm 7$  days) for patients with stable disease or better. Scans may also be conducted at any time, if clinically indicated.
- Study labs include: CBC with diff, alkaline phosphatase, albumin, total bilirubin, BUN, creatinine, calcium, glucose, AST, ALT, and electrolytes. These study safety labs are to be conducted within  $\leq 2$  weeks prior to registration.
- Testosterone level only at baseline.
- Assessment of response to therapy with PSA will occur on day 1 of odd cycles.
- Required for all patients at baseline and C3D1. Then only as clinically indicated thereafter.
- Blood will be collected at baseline, cycle 5 day 1, and at end of treatment for additional molecular analysis (see section 9).

**NU Study Number:** NU 18U10

8. Permission to obtain archival tissue samples of primary lesion and metastatic lesion sites will be obtained at baseline. The samples themselves will be collected only if available and only when requested by the Principal Investigator or Principal Investigator's designee; they may be collected at any time during the study, per PI request. Refer to the lab manual for details.
9. If there is concern about transformation to small cell cancer histology then a standard of care biopsy may be appropriate given that this is an exclusion criteria for this trial.
10. If tumor tissue is biopsied or resected as part of standard medical care or assessment from the time of study enrollment until progression then archival tissue from this biopsy/resection may be used for assay of the markers defined within the protocol to document molecular pathway characteristics and immune cell infiltration at that point to correlate with whether the cancer is responding, stable or progressing.
11. Patients will receive sEphB4-HSA 1000mg IV (60min infusion) on day 1 of each cycle along with continuation of androgen deprivation therapy. Refer to Table 4-2-1 for required premedication regimens.
12. Imaging must be completed and reviewed within 6 days (whenever feasible) prior to receiving treatment.
13. **Please see Table Below.** Beginning at Cycle 7, cycle length will be 21 days and patients will return for treatment on Day 1 of each cycle.
14. Patients will return for an End of Treatment (EOT) visit 30 ( $\pm 3$ ) days of the last dose of study treatment or prior to start of new treatment.
15. If off treatment for reasons other than disease progression, patients will be followed every 6 months, until objective progression or patient starts alternative therapy for a maximum of 1 year.
16. If patient has had molecular testing (i.e., NGS testing, genetic testing, genomic testing, etc.) performed as standard of care prior to study entry or at any time during study participation, collect a copy of the results report for correlative analyses. Refer to Section 9 for details.
17. Screening/baseline assessments are to be conducted within 1 month prior to registration unless otherwise indicated.

## Study Calendar Beginning at Cycle 7

Time Period	On Treatment (1 Cycle = 21 Days)						Off Treatment	
	Cycle 7	Cycle 8	Cycle 9	Cycle 10	Cycle 11	Cycle 12+	End of Treatment 	Follow-up 
	Week 13 Day 1	Week 16 Day 1	Week 19 Day 1	Week 22 Day 1	Week 25 Day 1	Week 28 Day 1		
Assessment or Activity								
Informed Consent								
Medical history 							X 	
Physical exam 	X	X	X	X	X	X	X	
ECOG status	X	X	X	X	X	X	X	
Toxicity assessment	X	X	X	X	X	X	X	
Review Concomitant Medications	X	X	X	X	X	X	X	
Tumor Imaging 				X 			X	
CBC + diff, chemistry, liver enzymes *,3, 4	X	X	X	X	X	X	X	
PSA *,5	X	X	X	X	X	X	X	
EKG *,6				As clinically indicated				
Research blood 							X	
Archival tissue sample 					X			
sEphB4-HSA administration 	X	X	X	X	X	X		
Survival Status								X

\*Can be completed  $\pm 3$  days of drug administration

- Includes vital signs (pulse, blood pressure) and height (baseline only) and weight.
- Bone scan, CXR or CT of chest, CT or MRI or abdomen and pelvis; with IV contrast if renal function adequate; the same modality used at baseline should be used throughout as clinically indicated.
- Study labs include: CBC with diff, alkaline phosphatase, albumin, total bilirubin, BUN, creatinine, calcium, glucose, AST, ALT, and electrolytes.
- Testosterone level only at baseline.
- Assessment of response to therapy with PSA will occur on day 1 of each cycle.
- Required for all patients at baseline and C3D1. Then only as clinically indicated thereafter.
- Blood will be collected at baseline, cycle 5 day 1, and at end of treatment for additional molecular analysis (see section 9).
- Permission to obtain archival tissue samples of primary lesion and metastatic lesion sites will be obtained at baseline. The samples themselves will be collected only if available and only when requested by the Principal Investigator or Principal Investigator's designee; they may be collected at any time during the study, per PI request. Refer to the lab manual for details.
- If there is concern about transformation to small cell cancer histology then a standard of care biopsy may be appropriate given that this is an exclusion criteria for this trial.
- If tumor tissue is biopsied or resected as part of standard medical care or assessment from the time of study enrollment until progression then archival tissue from this biopsy/resection may be used for assay of the markers defined within the protocol to document molecular pathway characteristics and immune cell infiltration at that point to correlate with whether the cancer is responding, stable or progressing.
- Patients will receive sEphB4-HSA 1000mg IV (60min infusion) on day 1 of each cycle along with continuation of androgen deprivation therapy. Refer to Table 4-2-1 for required premedication regimens.
- Imaging must be completed and reviewed prior to receiving treatment.

**NU Study Number:** NU 18U10

13. Imaging will occur at baseline and 2 months ( $\pm$  7 days) after starting therapy; thereafter, imaging will be conducted every 3 months ( $\pm$  7 days). After 1 year, imaging can be done every 4 months ( $\pm$  7 days) for patients with stable disease or better. Scans may also be conducted at any time, if clinically indicated.
14. Patients will return for an End of Treatment (EOT) visit 30 ( $\pm$ 3) days of the last dose of study treatment or prior to start of new treatment. If off treatment for reasons other than disease progression, patients will be followed every 6 months, until objective progression or patient starts alternative therapy for a maximum of 1 year.
15. If off treatment for reasons other than disease progression, patients will be followed every 6 months, until objective progression or patient starts alternative therapy for a maximum of 1 year.
16. If patient has had molecular testing (i.e., NGS testing, genetic testing, genomic testing, etc.) performed as standard of care prior to study entry or at any time during study participation, collect a copy of the results report for correlative analyses. Refer to Section 9 for details.

**NU Study Number:** NU 18U10

